#### **5.8.8. Assessment of Residual Confounding**

*Residual confounding of our VE estimates due to inadequate control for health care seeking behavior and immune status in our analyses will be explored. To do so, we will employ a negative control exposure and a negative control outcome. Potential negative control exposures include vaccinations that are recommended for PLWH but would not be expected to have any protective effect against the pneumonia outcomes of interest. We plan to use recombinant zoster vaccine (RZV) as the negative control exposure. Current US clinical guidelines recommend that PLWH be offered RZV vaccination. Therefore, we will develop a*

*model for our study population in which the exposure is at least one dose of RZV and the outcomes are our primary outcomes of interest. If residual confounding does not exist, RZV would not have an effect on the pneumonia outcomes. However, if the analysis demonstrates that RZV protects against these outcomes, this suggests the presence of residual confounding. Patients who have evidence of RZV during the six-month baseline period will be excluded from the negative control exposure analysis.*

*Similarly, potential negative control outcomes are outcomes that share the same sources of biases as the primary outcomes in our study population but are not causally-related to PCV13 vaccination. For example, immune status is an important predictor of pneumonia outcomes among PLWH, but we will be missing CD4 laboratory values for most of our study population. In order to detect potential residual confounding by lack of control for immune status, a potential negative control outcome could include a more common AIDS defining illness such as candidiasis. Again, if no residual confounding exists, PCV13 vaccination would have no effect on the occurrence of the negative control outcomes. However, if the results suggest that PCV13 vaccination prevents the negative control outcomes, residual confounding may exist.*

If the negative control outcome analysis indicates residual confounding, the results of the main outcomes may be additionally reported after correcting for the bias [12].

#### **5.8.9. Eligibility, Demographic, Clinical and Exposure Characteristics**

The number and percentage of patients meeting the eligibility criteria will be reported in a subject evaluation table overall and by index calendar year.

Descriptive statistics will be used to summarize patient demographics and clinical characteristics of all PLWH using values at index date by vaccination status by the end of the baseline period. Overall SMDs will be presented before and after IPTW. SMDs at the end of each year since follow-up will also be tabulated.

Summaries of the overall follow-up time will be presented and calculated as time from index date to the earliest of death, end of health plan enrollment, or end of study period.

The number of patients who receive PCV13 by the end of the overall follow-up will be reported. Kaplan-Meier analysis will be used to summarize the percentage of persons who receive PCV13 by the end of each year of follow-up from index date. Patients will be censored at the earliest of the following: death, end of health plan enrollment, or end of study period.

The overall distributions of the IPT, IPC and IPT\*IPC weights will be summarized by vaccination status. To graphically assess the IPT weights over time a plot of the distributions of the log-transformed stabilized weights may also be presented at regular (e.g. six-monthly) intervals during the follow-up.

The above analysis will be repeated by the subgroups stated in Section 5.2.3.

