9.5. Study Size

The planned analyses do not involve hypothesis testing and sample size calculations are not applicable. However, we examined the precision of PCV13 vaccine effectiveness for IPD and all-cause pneumonia among people living with HIV at 36 months and 97 months (which was the maximum follow-up time available from feasibility assessments) after index (Table 2 and Table 3). Komodo Health provided the following information for the precision estimates:

- 175,000 individuals had ≥ 1 inpatient or ≥ 2 outpatient HIV ICD-9-CM or ICD-10-CM code diagnosis codes between January 1, 2014 and December 31, 2021
- 56,000 (32%) of these individuals received PCV13 after their first HIV diagnosis code

The following assumptions regarding incidence and PCV13 VE for IPD and all-cause pneumonia were used:

- IPD incidence among PLWH is 183 cases per 100,000 population [28]
- All-cause pneumonia incidence among PLWH is 5,487 cases per 100,000 population
- VE for IPD due to any serotype ranges from 7.5% to 22.5%
 - Published VE estimates for vaccine type IPD range from 25% to 75% [20]. Because one-third of the adult IPD burden is considered PCV13 type [29], we multiplied this range by 30% to arrive at 7.5% to 22.5%
- VE for all-cause pneumonia ranges from 5% to 15% [30]
- Annual censoring of individuals due to loss to follow-up or death may range between 4% or 10%

Survival and censoring times were simulated assuming exponential distributions. Vaccination status was modelled as a time-varying covariate [31]. Hazard ratios were assumed as $1 - (VE/100)$. Simulations were run 100 to 200 times per scenario. Cox regression models were run on each simulated dataset to estimate the 95% confidence

PFIZER CONFIDENTIAL

intervals (CI) for the log HRs. Means were generated and exponentiated to obtain the 95% CIs for the VEs using $(1 - HR) \times 100$ and used to describe VE precision.

Table 2. Precision of PCV13 vaccine effectiveness estimates for invasive pneumococcal disease

Hypothesized Vaccine Effectiveness (%)	36 months of follow-up			97 months of follow-up		
	Lower 95% confidence interval estimate	Upper 95% confidence interval estimate	Total number of events	Lower 95% confidence interval estimate	Upper 95% confidence interval estimate	Total number of events
Scenario #1 – 4% annual censoring						
7.5	-12	25	837	-5	19	1492
22.5	3	37	817	11	33	1452
Scenario #2 – 10% annual censoring						
7.5	-15	25	766	-6	21	1272
22.5	2	38	752	9	33	1224

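### Yearly PCV13 uptake is estimated by Kaplan-Meier with death censored, so the reported percentage is uptake in the absence of death and runs somewhat high in later years

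*SAP*

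**What the plan says.** SAP 5.8.9 plans two summaries of exposure. The first is a count: "The number of patients who receive PCV13 by the end of the overall follow-up will be reported". The second is a yearly percentage measured from index: "Kaplan-Meier analysis will be used to summarize the percentage of persons who receive PCV13 by the end of each year of follow-up". For this curve, "Patients will be censored at the earliest of the following: death, end of health plan enrollment, or end of study period". The section closes with "The above analysis will be repeated by the subgroups stated in Section 5.2.3", so the yearly percentages are also produced by PPSV23 receipt, CD4 category, ART adherence, year of HIV diagnosis and age, where those subgroup analyses go ahead.

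Neither document names a competing-risk method, and neither describes the percentage as conditional on survival or as uptake in the absence of death. On attrition, Protocol 9.5 gives one combined assumption: "Annual censoring of individuals due to loss to follow-up or death may range between 4% or 10" per cent. Deaths are not separated from other loss. Protocol 9.4 and SAP 5.4 say that the data source holds mortality information.

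**The concern.** Censoring suits people whose later vaccination is possible but unseen, such as those who leave the health plan. It does not suit people who have died, because no later vaccination exists to be missed. Kaplan-Meier in effect gives the dead the vaccination rate of those still under observation. The result answers what share would be vaccinated if nobody died. The SAP's label describes a different quantity, the share of persons who receive PCV13.

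The yearly percentages tell readers how much of the cohort was exposed and when. With about 175,000 people they will carry narrow confidence intervals, so even a modest bias will not be visible as imprecision. Because the analysis is repeated by subgroup, the overstatement will also differ between groups to the extent that their mortality differs.

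**Working it through.** **The plan's own uptake figure.** Protocol 9.5 reports that "175,000 individuals had ≥ 1 inpatient or ≥ 2 outpatient HIV ICD-9-CM or ICD-10-CM code diagnosis codes" and that "56,000 (32%) of these individuals received PCV13 after their first HIV diagnosis code". Indeed 56,000 / 175,000 = 0.320. The documents state no Kaplan-Meier uptake figure and no death rate.

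**Inputs**
- From Protocol 9.5: N = 175,000; crude uptake 32%; total attrition *a* of 4% or 10% per year; maximum follow-up 97 months; and constant hazards ("Survival and censoring times were simulated assuming exponential distributions").
- Assumed: death rate *m*, shown from 0.2% to 2% per year and counted within *a*.
- Assumed: entry pattern, which is not given. Three were used: everyone has 97 months available; 40% have 97 months and the rest are spread evenly between 3 and 97 months; all are spread evenly.
- Simplification: all doses behind the 32% are placed after index. If some were given during the baseline period, the post-index vaccination rate, and with it the gap, would be smaller.

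**Formulas**, with vaccination hazard *v* and time *t* in years:
- One minus Kaplan-Meier, death censored: 1 − exp(−*vt*)
- Cumulative incidence with death competing: [*v*/(*v*+*m*)] × [1 − exp(−(*v*+*m*)*t*)]
- *v* is set so that crude observed uptake equals 32%. With 97 months for everyone this means [*v*/(*v*+*a*)] × [1 − exp(−(*v*+*a*) × 97/12)] = 0.32.

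**Worked case**, *a* = 4%, 97 months for everyone. Then *v* = 0.0571. At *m* = 1% and year 7:
- Kaplan-Meier: 1 − exp(−0.400) = 32.97%
- Cumulative incidence: (0.0571/0.0671) × (1 − exp(−0.470)) = 31.92%
- Gap: 1.05 points

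A simulation of 175,000 people with the same inputs gave 32.97% against 31.93%.

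**Year 7 at the two ends of the scenarios** (gaps taken before rounding). The lowest gap comes from 4% attrition with 97 months for all (*v* = 0.0571, Kaplan-Meier 32.97%). The highest comes from 10% attrition with evenly spread entry (*v* = 0.1312, Kaplan-Meier 60.07%).

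| Assumed deaths per year | Cumulative incidence, low case | Gap | Cumulative incidence, high case | Gap |
|---|---|---|---|---|
| 0.2% | 32.75% | 0.21 | 59.72% | 0.36 |
| 0.5% | 32.44% | 0.53 | 59.19% | 0.88 |
| 1% | 31.92% | 1.05 | 58.32% | 1.75 |
| 2% | 30.91% | 2.06 | 56.65% | 3.42 |

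**Growth with time** at *m* = 1%, low to high case: 0.03 to 0.06 points at year 1, 0.23 to 0.45 at year 3, 0.58 to 1.06 at year 5, 1.05 to 1.75 at year 7. At year 1 the gap stays at or below 0.12 points even with 2% deaths.

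**Against sampling error.** The Greenwood standard error at year 7 is about 0.12 to 0.24 points. The gap passes 2 standard errors at an assumed death rate of about 0.22% to 0.28% per year, and 5 standard errors at about 0.56% to 0.69%.

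**Subgroups.** For a group of 22,000, the smallest size in SAP Table 5.1, with an assumed 3% deaths per year and the same vaccination rate, the year-7 gap is 3.0 to 5.0 points (7 to 9 standard errors). For an assumed group of 2,000 with 5% deaths it is 4.8 to 8.0 points but only 3.5 to 4.3 standard errors.

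**The case against.** The strongest objection is that nothing of consequence depends on this output. All five objectives concern VE, and the Kaplan-Meier percentage feeds neither the weights nor the outcome models. The raw number vaccinated is reported as well. This stands, and it sets the priority. The raw count does not replace the yearly figure, though: it is one total at the end of follow-up, with no allowance for unequal follow-up.

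Second, Kaplan-Meier with death censored has a legitimate reading as uptake in the absence of death, if death is independent of vaccination. It also parallels the vaccination models behind the weights, where follow-up likewise ends at death. That is why relabelling is an acceptable alternative. The present label claims something else.

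Third, the comparison concerns vaccination recorded in claims. Protocol 9.9 accepts that some doses are given when claims are unavailable, which lowers measured uptake. The net error against true uptake is therefore unknown. This stands, but it does not justify a second error in the other direction.

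Fourth, SAP 5.8.4 accepts that censoring may be informative and plans censoring weights for the VE models, while the uptake curve has none. Treating death as a competing event does not resolve informative disenrollment. It also relies on death capture, whose completeness neither document states.

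A reader might also infer that the percentages are wrong by many standard errors. The documents do not support that. It needs a death rate they do not give: at 0.2% per year the year-7 gap is 1.5 to 1.8 standard errors. The count in standard errors also mainly reflects the cohort size.

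**Conclusion.** The estimator and its label do not match. With deaths before vaccination, one minus Kaplan-Meier must exceed the percentage of persons with a recorded PCV13 dose, and the gap widens with follow-up. At year 7 in the full cohort, across both attrition rates and all three entry patterns, it is about 0.2 to 0.4 points at 0.2% deaths per year, 0.5 to 0.9 at 0.5%, 1.1 to 1.8 at 1% and 2.1 to 3.4 at 2%. These figures assume constant hazards and an uptake rate calibrated to 32%.

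Two further inferences go beyond the documents. One is that subgroup comparisons of uptake are materially distorted. In percentage points the overstatement is larger where mortality is higher, but no subgroup death rates are given and no formal comparison of uptake between subgroups is planned. The other is that VE is biased, which does not follow because this output enters no VE estimate. The point is a minor correction to a descriptive table.

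**What to change.** In SAP 5.8.9, overall and by subgroup, replace the Kaplan-Meier percentage with the Aalen-Johansen cumulative incidence of PCV13 receipt. Treat death before vaccination as a competing event, and censor only at end of health plan enrollment or end of study. If Kaplan-Meier is kept, label the output in the text and table shells as uptake in the absence of death.

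The cost is about a sentence in the SAP and a few lines of R. The survival package that Appendix B already loads can produce the estimate from a multi-state status variable; Appendix B contains no Kaplan-Meier code to rewrite. No new data are needed, since death already ends follow-up. The downsides are slightly lower reported uptake and reliance on how completely the source captures deaths, which the report should state.

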#### 5.8.10. Summaries of Study Outcomes

The number of patients with each study outcome will be presented by vaccination status at the time of infection (Table 5.2). Length of follow-up by PCV13 vaccination status will be presented by summarizing person-time before and after any PCV13 vaccine. Crude incidence rates and 95% CIs will be presented PCV13 vaccination status for each outcome for first episodes and again including recurrent episodes of the same type.

The above analysis will be repeated by the subgroups stated in Section **Error! Reference source not found..**

#### 5.8.11. Analysis of Study Objectives

Crude HRs for PCV13 vaccination and the corresponding VE percentages will be presented together with 95% CIs for each study outcome overall and again during specific time periods (0-3, 3-5, 5-7 years). This will be done for first events and again including recurrent events. Analysis will be repeated using Cox-MSM after applying IPT and the IPT\*IPC weights.

The above analysis will be repeated by the subgroups stated in Section **Error! Reference source not found..**

#### 5.8.12. Analysis of Negative Control Outcomes and Exposure

The number of patients with the negative control outcome(s) will be presented by PCV13 vaccination status at the time of occurrence. Crude incidence rates and 95% CIs will be presented by PCV13 status for first and recurrent (separated by at least 90 days) episodes. Unadjusted and Cox-MSM will be used to obtain crude and weighted VE estimates and 95% CIs of PCV13 on candidiasis.

The number of patients who receive at least one dose of RZV by the end of the overall follow-up will be reported. Patients will be considered vaccinated with RZV 14 days after their vaccination date. Unadjusted and Cox-MSM will be used to obtain crude and weighted VE estimates and 95% CIs of RZV on each of the study outcomes of interest. Cox-MSM will additionally adjust for the main exposure of PCV13 as a time-varying covariate. Patients who have evidence of RZV before the six-month baseline period will be excluded from the negative control exposure analysis.

Weighted 95% CIs for the VEs that exclude 0% would suggest the presence of residual confounding in the weighted models between PCV13 and the study outcomes. If so, the results for the main outcomes may be corrected for bias identified from the negative control outcome.

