### 5.3.2. Covariates

The list of demographic and clinical characteristics considered for descriptive reporting, subgroups and inclusion as covariates in models for generating the propensity scores are provided in Table 5.3. The Komodo Health database will be source of all variables.

Patients will be considered to have a comorbidity or hospitalization during baseline if there was evidence of a diagnosis at any time during the baseline period. Evidence of comorbidities or hospitalization during follow-up will be considered as new diagnoses. Once diagnosed, patients will be considered diagnosed for the remainder of their follow-up. ART adherence during baseline and follow-up will be updated every 6 months (180 days) based on the data collected in that previous timeframe. For baseline annual physical exam and annual influenza vaccine, patients will be considered adherent (coded as 'Yes') if there was evidence of these events at any time during the baseline period. During the follow-up, patients will be considered adherent up to 365 days after the last event date.

For annual CD4 and viral load laboratory tests during baseline and follow-up, patients will be coded as 'Yes' up to 365 days after the last event date. For respiratory virus season during follow-up, patients will be coded as 'Yes' if the observation time is in October, November, December, January, February, March or April.

The baseline period for the assessment of covariates is the six months prior to the index date, i.e., no data prior to six months will be included.

Covariates used at baseline only will be considered time-fixed confounders. Covariates additionally or only used during follow-up will be considered time-varying confounders.

Categories may be collapsed, or covariates may be excluded from the propensity scores if models fail to converge.

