#### **5.8.4. Inverse Probability of Treatment Weighting for Time-Varying Exposures**

Except for patients vaccinated more than 13 days before the end of the baseline period, exposure (vaccination) status will not be fixed at start of follow-up, with patients able to receive PCV13 during follow-up. Therefore, PCV13 will be considered a time-varying exposure. The values for some clinical characteristics may also change during the study period and values during baseline may be poor proxies for covariate values at the various points during the follow-up. Therefore, some covariates will be treated as time-varying confounders (Section 5.3.2).

Inverse probability of treatment weighting (IPTW) will be generated from predicted probabilities of vaccination status (propensity scores) to create pseudo-populations where any imbalances in the potential confounders by vaccination status are reduced. For the analyses of first events, stabilized weights will be generated for each patient for the baseline period and every 30 days from index during the follow-up until the earliest of the following: outcome, death, end of health plan enrollment or end of study period. For the analyses of recurrent events, stabilized weights will be generated for each patient for the baseline period and every 30 days from index during the follow-up until the earliest of the following: death, end of health plan enrollment or end of study period. This aims to make vaccination status independent of the measured confounders at each of the follow-up timepoints [9]. The weights will be used to estimate the average treatment effect (ATE). For the analysis of RZV, stabilized weights will be generated every 90 days instead of 30, due to the expected lower numbers of patients vaccinated with RZV overall and in each interval.

The numerators for the stabilized weights will be the estimated probability of a patient's observed vaccination status at timepoint given their prior vaccination status and time-fixed covariates. The denominators will be the estimated probability of a patient's observed vaccination status at the given timepoint given their prior vaccination status, time-fixed covariates and time-varying covariates. Numerators and denominators after vaccination will be set to 1 and the cumulative product of these ratios will be calculated, therefore IPT

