#### **5.8.7. Vaccine Effectiveness**

Crude PCV13 VE percentages will be estimated based on  $(1-HR) \times 100$ , where HR is obtained from unadjusted Cox models for first episodes for each outcome. VE percentages will also be obtained from marginal structural Cox models (Cox-MSM) after applying the IPT and the IPT\*IPC weights. As the numerators for the stabilized weights will include the index-fixed covariates, those covariates will also be included in the Cox-MSM for the outcomes [9]. Cluster robust standard errors will be used to account for the multiple records per patient. The proportional hazards assumption will be assessed graphically with the inspection of Schoenfeld residuals.

To explore potential changes in VE over time, HRs may also be generated during specific time periods using piecewise Cox models. The time periods will be 0-3 years (0 to 1079 days), 3-5 years (1080 to 1799 days), 5-7 years (1800 to 2549 days).

VE may also be assessed for recurrent events using the Andersen-Gill (AG) model [11]. For each outcome, subsequent events will be of the same type, e.g., in the analysis of IPD it will be assumed that a patient is only at risk for future IPD events. The VE is assumed constant across the recurrent events.

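### The RZV negative-control model conditions on time-varying PCV13, but the RZV weights omit PCV13; if the two uptakes are linked, the all-cause pneumonia test can mislead

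*SAP*

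**What the plan says.** SAP 5.8.12 states that in the RZV analysis "Cox-MSM will additionally adjust for the main exposure of PCV13 as a time-varying covariate". SAP 5.8.7 uses the term Cox-MSM for the Cox outcome model fitted after the weights are applied, so on the plain reading PCV13 is a term in that model.

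SAP 5.8.4 gives one weight recipe for both vaccines. The numerator is the probability of observed vaccination status "given their prior vaccination status and time-fixed covariates"; the denominator is the same probability "given their prior vaccination status, time-fixed covariates and time-varying covariates". The only change for RZV is the interval: "For the analysis of RZV, stabilized weights will be generated every 90 days instead of 30". SAP 5.3.2 says that the variables considered for "inclusion as covariates in models for generating the propensity scores are provided in Table 5.3", and PCV13 is not in that table. The example code in Appendix 7.2.2 builds weights for PCV13 and for censoring only. No section writes out the RZV weight model, so the omission of PCV13 is read from these parts together.

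SAP 5.8.7 also ties the outcome model to the weight numerators: "As the numerators for the stabilized weights will include the index-fixed covariates, those covariates will also be included in the Cox-MSM for the outcomes". In the RZV analysis PCV13 departs from that pattern.

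On interpretation, SAP 5.8.8 says: "However, if the analysis demonstrates that RZV protects against these outcomes, this suggests the presence of residual confounding". SAP 5.8.12 takes a weighted interval that excludes 0% as the signal and allows an optional correction of the main results.

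**The concern.** The stated null is that, without residual confounding, RZV has no effect on the pneumonia outcomes. The RZV weights are meant to make RZV uptake independent of the time-varying covariates overall. They do not guarantee this within levels of PCV13. PCV13 uptake depends on the same covariates and may be linked to RZV uptake. Once PCV13 is held fixed in the outcome model, RZV can again be associated with risk factors that the model does not contain.

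The RZV estimate could then differ from the null although every confounder was measured. It would be read as evidence against the PCV13 estimates. A bias in the opposite direction could cancel a real signal.

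**Working it through.** **Step 1. Where PCV13 enters the RZV analysis**

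| Component | Contains PCV13? | Source |
|---|---|---|
| RZV weight numerator | No | SAP 5.8.4, Table 5.3 |
| RZV weight denominator | No | SAP 5.8.4, Table 5.3 |
| Separate PCV13 weight | Not applied | SAP 5.8.4, 5.8.12 |
| Outcome model | Yes, time-varying | SAP 5.8.12 |
| Balance check | Not stratified by PCV13 | SAP 5.8.5 |

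**Step 2. Mechanism.** Let L be a measured time-varying risk factor. PCV13 depends on L, and PCV13 and RZV are linked given L. Holding PCV13 fixed then associates RZV with L. L affects the outcome and is not in the outcome model. SAP 5.8.5 allows imbalanced covariates to be added, but its overall SMDs would not show an imbalance that exists only within PCV13 strata. If L raises PCV13 uptake and the link is positive, RZV looks protective; if L lowers uptake, RZV looks harmful. Without a link nothing happens.

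**Step 3. Calibration.** The plan gives no figure for the RZV analysis. As a check of scale, the half-width on the log HR is 1.96/√(D·q(1−q)), with D the 97-month event counts at 4% censoring (Protocol 9.5, Tables 2 and 3) and q = 0.20 an assumed vaccinated share of person-time.
- All-cause pneumonia, VE 5%: D = 38,848, half-width 0.0249, interval 2.6 to 7.3 (stated 2 to 7).
- IPD, VE 7.5%: D = 1,492, half-width 0.127, interval −5.0 to 18.5 (stated −5 to 19).

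**Step 4. Main simulation.** From the documents: 175,000 people, PCV13 uptake about 32%, PCV13 VE 15% (all-cause pneumonia) or 22.5% (IPD), 4% annual censoring, 90-day intervals. Assumed: RZV uptake about 7% to 14%, outcome HR of 3 for L, effect of L on uptake ×0.5 to ×3, and the links below. The true RZV HR is 1 and L is fully measured. There were 40 replicates per scenario and about 40,000 all-cause pneumonia events.

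Signal probability = 1 − Φ(1.96 − |μ|/s) + Φ(−1.96 − |μ|/s), with μ the mean log HR and s its SD. For the two-way ×2 link, μ = ln(1 − 0.0259) = −0.0262 and s = 0.0203, so |μ|/s = 1.29 and the probability is 1 − Φ(0.67) + Φ(−3.25) ≈ 0.25.

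| Scenario | As planned: RZV VE (signal) | Joint weights: RZV VE (signal) |
|---|---|---|
| No link given L | 0.45% (6%) | 0.44% (6%) |
| PCV13 doubles RZV uptake | 1.58% (10%) | 0.40% (5%) |
| Two-way link ×2 | 2.59% (25%) | −0.10% (5%) |
| 10% same-interval co-administration | 3.68% (46%) | 0.96% (7%) |
| Two-way ×3, L triples PCV13 uptake | 7.01% (91%) | −0.21% (5%) |
| Two-way ×2, L halves uptake of both | −2.41% (11%) | −0.90% (6%) |
| Two-way ×2, PCV13 without effect | 1.61% (10%) | −0.82% (6%) |
| Two-way ×2, IPD-sized (1,533 events) | 2.15% (5%) | −0.28% (5%) |

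The Monte Carlo SE is 0.3 to 0.5 points for all-cause pneumonia and 1.9 for IPD. The row with PCV13 without effect shows that the bias is not just PCV13 protection credited to RZV. In the IPD row s is 0.122, so |μ|/s is only 0.0217/0.122 = 0.18.

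Adding PCV13 to the RZV numerator and denominator alone left 1.45% with the ×2 link and 3.66% with the ×3 link, because PCV13 can follow RZV.

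**Step 5. Simulation with other inputs** (RZV uptake 4% to 7%, outcome HR 2.5 for the risk factor, PCV13 VE 15%). Strong linkage, with RZV recipients about 2.2 times as likely to have PCV13, gave an RZV HR of 0.964 and 34% rejection at nominal 5%. Moderate linkage gave about 0.98 and 12% to 13%. With the risk factor halving PCV13 uptake it gave 1.03 and 22%. Weak or no linkage gave about 5%. A further small check gave 1.005 without a link; under a weak link it gave 0.985 to 0.989 as planned against 0.992 to 0.998 with joint weights.

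**The case against.** The SAP never states the RZV weight model. Protocol 9.7 says that time-varying covariates are adjusted for through the weights, so the sentence in SAP 5.8.12 might mean that PCV13 joins the RZV weight denominator. The conditioning problem would then not arise. That reading is strained, because SAP 5.8.7 attaches the term Cox-MSM to the weighted outcome model. It would also leave RZV credited with PCV13 protection that follows it: 1.60% under the two-way ×2 link, against −0.77% when PCV13 has no effect.

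The inputs that drive the size are not in the documents. The link that matters is the one that remains given the measured covariates. Table 5.3 includes influenza vaccination, annual physical exam, hospitalization, ART adherence, and CD4 and viral load testing, all of which track care contact or vaccine acceptance. The simulations used one measured risk factor, so their links may be stronger than what would remain. This stands.

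The benefit of joint weights was not shown everywhere. In one scenario of the Step 5 simulation, with a tenfold co-visit effect, the HR was 0.973 as planned and 0.982 with joint weights, a difference within Monte Carlo error (about 0.009 on each HR). In the co-administration row of Step 4, joint weights still left 0.96%.

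Finally, this is a diagnostic, and no PCV13 estimate is computed from the RZV model. That also stands.

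**Conclusion.** The point holds as a conditional weakness in a diagnostic analysis. Followed as written, the plan conditions on PCV13 without weights that are valid given PCV13. With residual linkage between the two uptakes, the all-cause pneumonia test can signal or mask residual confounding. Spurious RZV effectiveness was roughly 1% to 4% under weak to strong assumed links, more under an extreme one, and could turn negative. Without a link there was none.

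Three stronger readings are tempting and are not supported:
- A reader might infer that conditioning on PCV13 always destroys the balance. It does so only if the uptakes are linked given the covariates, and the documents neither quantify nor exclude that.
- A reader might infer that all primary outcomes are affected alike. At the IPD event count the signal rate stayed near 5%. Pneumococcal pneumonia was not examined.
- A reader might infer that the RZV estimate would shift PCV13 effectiveness. SAP 5.8.8 and 5.8.12 take the correction from the negative control outcome and make it optional. A false RZV signal could affect interpretation and, on one reading of SAP 5.8.12 and under the broader wording of Protocol 9.9, whether a correction is made, but not its size under the SAP.

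**What to change.** In SAP 5.8.12, specify the RZV analysis as a joint marginal structural model:
- Put lagged PCV13 status in both the numerator and denominator of the RZV weight models.
- Re-estimate PCV13 weights on 90-day intervals with RZV status in those models. State whether that status is current or lagged, since both vaccines may be given in one interval.
- Multiply the two sets of weights, and the censoring weights, and use the product in the Cox model that contains both RZV and PCV13.
- Report covariate balance across RZV status within PCV13 strata.

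The cost is more than one multiplication. The planned PCV13 weights use 30-day intervals and omit RZV, and SAP 5.8.4 derives weights separately for each outcome, so new models are needed per outcome. The weights will be somewhat more variable. In the one-covariate simulation the SD of the log HR barely moved (0.0203 to 0.0202 for the two-way ×2 link, 0.0202 to 0.0208 for co-administration), but the full covariate list may cost more precision.
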